12.6.1.3 Bacterial, fungal and non-CMV viral infections

Invasive fungal infections, major bacterial infections and non-CMV viral infections will be analyzed. These infections are outlined in the manual of operations. The analysis of incidence of an opportunistic infection will be performed using a Chi Square test or Fisher Exact in the modified ITT population. Results will be reported as the p -value and the 95% confidence interval for the difference in the rates of invasive fungal, major bacterial or viral infections; the analysis will be repeated using a CMH test stratified by receipt of induction therapy. The analysis will include an assessment of baseline comparability of the comparison groups and will incorporate variables not adequately controlled by randomization. The initial episode of major infection will be evaluated in a time dependent Cox model with the end point being the date of first major infection. The starting point will be date of transplantation and the infection free survival functions will be compared between the two regimens adjusted for cluster [site]. Subjects will be censored at death and study termination/withdrawal. Multiple infection episodes will be evaluated by comparing the total 1 year episodes per person day of follow up between the two regimens. The analysis will be repeated controlling for receipt of anti-lymphocyte induction and renal dialysis. The type of infection (major bacterial, fungal, non- CMV viral) will be compared between the two regimens using a CMH test, non-stratified and controlled for induction antilymphocyte therapy and renal dialysis. Summary tables listing the type of opportunistic infections for each regimen will be presented.

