12.6.1.4 Allograft rejection

Rejection will be evaluated by several methods. Rejection rates at one year, between the two groups will be evaluated with a CMH test, both non-stratified and adjusted for receipt of antilymphocyte induction and renal dialysis. Initial rejection will be evaluated in a time dependent Cox model with the end point being the date first rejection episode. The starting point will be date of transplantation and the rejection free survival functions will be compared between the two regimens adjusted for cluster. Multiple rejection episodes will be evaluated by comparing the total 1 year episodes of rejection between the regimens using a regression model with the endpoint total number of rejection episodes, clustered by site, and adjusted for receipt of antilymphocyte induction therapy and renal dialysis. An additional model may be developed to adjust for inequalities not adequately controlled by the randomization process. Incidence of chronic graft rejection will be compared between the two study groups using a CMH test stratified for receipt of induction lymphocyte depleting therapy and controlling for renal dialysis.

Rejection episodes

Incidence rates will [number of rejection episodes per patient days of follow up] will be calculated and compared between the two groups. Patient days will be counted from the day of

randomization until the date of death, one year or last known follow up if subject is unable to be followed for one year.

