12.6.3 Adverse events

Severe, unexpected drug related adverse events will be compiled and compared between the two groups. Adverse events will be evaluated by comparing the total number of reportable adverse events per person day of follow up between the two regimens. The analysis

will be repeated stratified by receipt of anti-lymphocyte induction and renal dialysis using Mantel-Haenzel weights. The analysis will include assessment of baseline comparability of the comparison groups and if necessary, will adjust for items not adequately controlled by randomization in additional models.

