12.7.1.7 Opportunistic infections

Incidence rates [number of infections per patient days of follow up] will be calculated. Patient days will be counted from the day of randomization until the date of death, end of study or last known follow up if subject is lost to follow up. The rates will be compared between the two groups using both the ITT population and modified ITT populations. The incidence rate will be calculated for all OI combined. Separate rates will also be calculated for bacterial and fungal infections. Similar analyses will be done using the date of study closure as the endpoint.

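### The pooled events-per-person-day comparisons of infections, reportable adverse events and rejection episodes do not account for repeat events within a subject

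*Combined protocol and SAP*

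**What the plan says.** Four places in section 12 compare the arms on total events divided by total person-time:

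- **Infections (12.6.1.3):** "Multiple infection episodes will be evaluated by comparing the total 1 year episodes per person day of follow up between the two regimens". The repeat analysis controls for induction and dialysis.
- **Adverse events (12.6.3):** "Adverse events will be evaluated by comparing the total number of reportable adverse events per person day of follow up between the two regimens". This analysis "will be repeated stratified by receipt of anti-lymphocyte induction and renal dialysis using Mantel-Haenzel weights".
- **Rejection (12.6.1.4, paragraph on rejection episodes):** the rate is the "number of rejection episodes per patient days of follow up", compared between groups.
- **Opportunistic infections (12.7.1.7, exploratory):** "Incidence rates [number of infections per patient days of follow up] will be calculated", and the rates are then compared in the ITT and modified ITT populations.

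None of the four names a variance, an overdispersion term or clustering by subject. No test is named either, apart from the Mantel-Haenszel weights in 12.6.3.

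The plan also contains analyses that do not depend on repeat events. Infection has a chi-square or Fisher test, a CMH test, and a first-event analysis: "The initial episode of major infection will be evaluated in a time dependent Cox model". Rejection has a CMH test and a Cox model to first rejection. Total rejection episodes are also compared "using a regression model with the endpoint total number of rejection episodes, clustered by site", adjusted for induction and dialysis.

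**The concern.** Total events over total person-days, with Mantel-Haenszel weights for the stratified version, is the standard person-time method. Its variance is built from the event totals, so ten episodes in one subject count as much information as one episode in each of ten subjects. That is valid only if subjects share the same underlying rate. The protocol suggests otherwise: 9.4.1.1 describes a critically ill population with a high rate of untoward events, 2.2.2 stratifies for dialysis because of its higher mortality, and 12.6.1.3 itself provides for several infections per subject.

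Where the authors wanted a correlation method they named one: adjustment for site in the first-infection Cox model, site clustering in the rejection regression, and GEE and repeated-measures models for the immune assays (12.7.3). The rate comparisons have none. Stratifying by induction and dialysis removes differences between strata, not the remaining differences between subjects within a stratum.

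At stake is whether a few subjects with many episodes could make the strategies look different in infection burden or adverse-event rate when they are not.

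**Working it through.** The plan gives no episode rate, dispersion, standard error or power for these comparisons, so there is no figure of its own to reproduce.

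**Inputs from the documents.** Minimum 176 subjects (section 4), allocated 1:1 (12.2), so 176 / 2 = 88 per arm. Two-sided alpha 0.05 (12.4.1). Six sites (protocol summary).

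**Assumed inputs (not in the documents).** Mean episodes per subject μ from 0.3 to 1.5; dispersion k from 0 to 2, where the variance of a subject's count is μ(1 + kμ) (negative binomial); equal follow-up; no true difference between arms.

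**Step 1: standard error used by the pooled comparison.** With A and B total events, SE of the log rate ratio = √(1/A + 1/B). Expected A = B = 88μ, so SE = √(2 / (88μ)).

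**Step 2: true standard error.** An arm total has variance 88μ(1 + kμ), so the true SE is about √(2(1 + kμ) / (88μ)). The ratio of true to used SE is √(1 + kμ).

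**Step 3: true error of a 5% test.** 2 × [1 − Φ(1.96 / √(1 + kμ))].

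**Worked case, μ = 1, k = 1.** SE used = √(2/88) = 0.151; true SE = √(4/88) = 0.213; ratio 1.41. Around a rate ratio of 1, the pooled 95% limits are exp(±1.96 × 0.151) = 0.74 to 1.34. Correct limits are exp(±1.96 × 0.213) = 0.66 to 1.52. Error = 2 × [1 − Φ(1.386)] = 16.6%.

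**Step 4: simulation.** 20,000 null trials per setting, 88 per arm, gamma-Poisson counts. The same data were also tested with a between-subject variance.

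| μ | k | SE ratio | Error, formula | Error, pooled test (simulated) | Error, between-subject variance (simulated) |
|---|---|---|---|---|---|
| 0.3 | 0 | 1.00 | 5.0% | 4.7% | 5.0% |
| 0.3 | 0.5 | 1.07 | 6.8% | 6.5% | 5.0% |
| 0.3 | 2 | 1.26 | 12.1% | 11.6% | 5.5% |
| 0.5 | 1 | 1.22 | 11.0% | 10.9% | 5.7% |
| 1.0 | 1 | 1.41 | 16.6% | 16.0% | 5.2% |
| 1.5 | 2 | 2.00 | 32.7% | 32.2% | 5.8% |
| 1.5 | 0 | 1.00 | 5.0% | 5.1% | 5.3% |

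Formula and simulation agree. The inflation depends on the product kμ and vanishes at k = 0. A between-subject variance keeps the error between 4.9% and 5.8% over the whole grid at 88 per arm.

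**The case against.** The strongest reply is that the plan never says episodes are independent. A rate per person-day can be compared with a robust or overdispersed variance, and silence is not a method. This stands as far as it goes: a reader might infer that the plan adopts a Poisson variance, but no section states one. The consequence is therefore conditional on the comparison being run in its ordinary form. It remains the likely form, given Mantel-Haenszel weighting in 12.6.3 and no correlation method in any of the four places.

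A reader might also infer that repeat events are ignored throughout. For rejection they are not. The regression on episode totals, read as one count per subject with site-clustered errors, allows for correlation within a subject because subjects are nested in sites. Its model family is unnamed and six sites are few for a cluster-robust variance, but only the separate rate paragraph is at issue here.

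The listed secondary outcomes are incidences of infection and rejection (3.2.2). Their chi-square or Fisher, CMH and first-event analyses count one event per subject and are untouched, as is the primary endpoint; 12.7.1.7 is exploratory.

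For adverse events, the count is restricted. Only events that are unexpected after liver transplantation or thought to be drug-related are reportable (9.2.3), and Appendix C lists infection, sepsis and leukopenia among the expected ones. The window is treatment plus 7 days, about day 107 with prophylaxis (9.5). A low mean is plausible, which points to the smaller inflations in the table. Recurrence is still possible, since 7.5.3.1 makes each ANC below 1000/µL an adverse event. No one-event-per-subject analysis of reportable events overall stands behind the rate; neutropenia alone has its own CMH test (12.6.2.1).

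**Conclusion.** The point holds for the rate comparisons in 12.6.1.3, 12.6.3 and 12.7.1.7 and for the rejection-rate paragraph in 12.6.1.4. They leave repeat events within a subject unaccounted for. If run as ordinary person-time comparisons, their intervals are too narrow by a factor of about 1.07 to 2.00 on the log scale, and a 5% test errs about 6% to 32% of the time. This assumes μ of 0.3 to 1.5, k of 0.5 to 2, equal follow-up and 88 per arm. With no heterogeneity between subjects the error stays at 5%. The direction is secure whenever subjects differ in risk; the size is not, because the documents give neither mean nor dispersion, and one grid need not suit infections, rejection and adverse events alike.

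The adverse-event comparison is the most exposed, for want of a per-subject analysis behind it rather than because its inflation is known to be large.

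A reader might extend this to the second halting rule in 9.8.3, which acts on a difference in reportable SAEs significant at 0.05. That rule names no test and does not refer to 12.6.3, so the documents do not support saying that the inflation reaches it.

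**What to change.** For the rate comparisons in 12.6.1.3, 12.6.1.4, 12.6.3 and 12.7.1.7, specify a model with one count per subject, including subjects with zero events. Use either a negative binomial model with log follow-up time as offset, or a Poisson model with the same offset and a subject-level robust variance; name one in advance. Include terms for arm, lymphocyte-depleting induction and dialysis. Report the rate ratio with its 95% confidence interval and keep the crude events per person-day as description. For rejection, use this same model for both the episode-total regression and the rate comparison, so that one question does not have two answers.

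The cost is SAP wording and one model statement per endpoint. It uses data already collected and leaves the sample size alone. The downside is wider confidence intervals wherever episodes cluster in subjects.

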12.6.1.4 Allograft rejection

Rejection will be evaluated by several methods. Rejection rates at one year, between the two groups will be evaluated with a CMH test, both non-stratified and adjusted for receipt of antilymphocyte induction and renal dialysis. Initial rejection will be evaluated in a time dependent Cox model with the end point being the date first rejection episode. The starting point will be date of transplantation and the rejection free survival functions will be compared between the two regimens adjusted for cluster. Multiple rejection episodes will be evaluated by comparing the total 1 year episodes of rejection between the regimens using a regression model with the endpoint total number of rejection episodes, clustered by site, and adjusted for receipt of antilymphocyte induction therapy and renal dialysis. An additional model may be developed to adjust for inequalities not adequately controlled by the randomization process. Incidence of chronic graft rejection will be compared between the two study groups using a CMH test stratified for receipt of induction lymphocyte depleting therapy and controlling for renal dialysis.

Rejection episodes

Incidence rates will [number of rejection episodes per patient days of follow up] will be calculated and compared between the two groups. Patient days will be counted from the day of

randomization until the date of death, one year or last known follow up if subject is unable to be followed for one year.

12.6.1.5 Graft loss (loss due to retransplantation)

The incidence of retransplantation will be determined at the 3 and 12 month time points. The date of retransplantation will be considered the date of occurrence of the event. A Cochran-Mantel-Haenszel test stratified for receipt of antilymphocyte therapy and controlling for renal dialysis will be used to test the significance between the two treatment regimens.

12.6.1.6 All-cause mortality

A Kaplan-Meier survival probability will be calculated for each regimen. The starting point will be the date of randomization and the end point will be date of death. Subjects will be censored at date of last follow up if lost to follow up, or at one year post-transplant. The equality of the two survivor functions will be compared using a rank sum test for both the non-stratified data as well as the stratified log rank test for each stratum separately (receipt of lymphocyte depleting induction therapy and renal dialysis). Graphs of the Kaplan-Meier curves will be presented.

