12.7 Exploratory end-points

12.7.1 Clinical outcomes

12.7.1.1 Time to onset of CMV disease

Disease free survival will be evaluated by calculating the Kaplan-Meier survival probability for each regimen. The starting point will be the day of transplant; the end point will be the date of onset of CMV disease. Subjects will be censored at date of death if unrelated to CMV, date of last follow up if lost to follow up or at end of study. Kaplan-Meier estimates of median time to onset of CMV disease and the associated 95% confidence interval will be presented. In addition, the Kaplan-Meier estimates and associated confidence intervals will be presented for specific time points (100-day, 6-month 12-months) and quartiles (25th and 75th). The study groups will be compared using the non-stratified log rank test, as well as the stratified log rank test for each stratum separately. Graphs of the Kaplan-Meier curves for each therapy group will be presented. The equality of the two survivor functions will also be compared using a Cox model adjusted for cluster [site] and controlled for receipt of anti-lymphocyte induction therapy and renal dialysis. The primary analysis will include assessment of baseline comparability between the two treatment groups. If needed, additional models will be developed to adjust for inequalities not adequately controlled by the randomization process. Results will be reported as the hazard ratio comparing the 2 groups. Survival analyses will also be controlled for unequal follow up periods between subjects. As such, the number of subjects available at annual time points will be reported, along with the Kaplan-Meier probability and associated 95% confidence intervals. It is assumed that subjects censored early will have the same probability of disease at each time point as those with longer follow up. To examine this assumption, relevant baseline characteristics will be compared between subjects enrolled in the first half of the study with those enrolled later. If the 2 cohorts are similar, we can expect that the survival probabilities are valid even with difference in follow up. Disease free survival will also be examined between the two cohorts.

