12.7.1.2 Composite disease free survival

A Kaplan-Meier survival probability will be calculated for each regimen. The starting point will be the day of transplant; the end point will be the date of onset of CMV disease or date of death. Subjects will be censored at date of last follow up if lost to follow up, withdrawal or at end of study. The equality of the two survivor functions will be compared using a rank sum test for both the nonstratified grouping and the stratified by receipt of antilymphocyte induction therapy and renal dialysis.

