12.7.1.4 Graft loss [retransplantation]

A Kaplan-Meier survival probability will be calculated for each regimen. The starting point will be the day of transplant; the end point will be the date of retransplant. Subjects will be censored at date of last follow up if lost to follow up, at date of death, or at study closure (and no longer than 7 years after enrollment). The equality of the two survivor functions will be compared using a rank sum test. Additional models will include adjustment for cluster [site] and receipt of antilymphocyte induction therapy and renal dialysis. The analysis will include assessment of baseline comparability between the two treatment groups. If needed, additional models will be developed to adjust for inequalities not adequately controlled by the randomization process.

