12.7.1.6 All-cause mortality

A Kaplan-Meier survival probability will be calculated for each regimen. The starting point will be the date of randomization and the end point will be date of death. Subjects will be censored at date of last follow up if lost to follow up, or at study closure (and no longer than 7 years after enrollment). The equality of the two survivor functions will be compared using a rank sum test for both the non-stratified data as well as the stratified log rank test for each stratum separately (receipt of lymphocyte depleting induction therapy and renal dialysis). The number of subjects available at annual time points will be reported, along with the Kaplan-Meier probability and associated 95% confidence intervals. To validate the assumption of that all subjects have similar probability of survival at each time point despite different follow up, relevant baseline characteristics will be compared between subjects enrolled in the first half of the study with those enrolled later. If the 2 cohorts are similar, we can expect that the survival probabilities are valid irrespective of variable follow up. Survival will also be examined between the two cohorts.

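### A rank sum test is named for censored survival comparisons where 12.7.1.1 uses the log-rank test; the test is not identified, and an ordinary rank sum test could cost much of the power

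*Combined protocol and SAP*

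**What the plan says.** Four sections of the combined protocol and SAP define Kaplan-Meier curves, give censoring rules, and then name a rank sum test for the comparison of arms:

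- 12.6.1.6, one-year mortality (secondary): "compared using a rank sum test for both the non-stratified data as well as the stratified log rank test for each stratum separately".
- 12.7.1.2, CMV disease or death (exploratory): "The equality of the two survivor functions will be compared using a rank sum test for both the nonstratified grouping", and again for the stratified comparison.
- 12.7.1.4, retransplantation to study closure (exploratory): "The equality of the two survivor functions will be compared using a rank sum test", with adjusted models in addition.
- 12.7.1.6, mortality to study closure (exploratory): "compared using a rank sum test for both the non-stratified data", again with a log-rank test by stratum.

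The same test name appears for time to G-CSF (12.7.2.2) and for time to late CMV disease by antibody status (12.7.3.2). For time to CMV disease, 12.7.1.1 says instead: "The study groups will be compared using the non-stratified log rank test, as well as the stratified log rank test for each stratum separately". No section defines the rank sum test.

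**The concern.** An ordinary rank sum (Mann-Whitney) test ranks the observed follow-up times and does not use whether each time ended in an event or in censoring. Most subjects in these analyses will be censored, so much of the ranking would come from follow-up length, which carries no information about outcome.

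The two mortality sections also use different tests for the unstratified and stratified comparisons, with no reason given. An analyst could defend either test, and could choose after seeing the data. What is at stake is a missed difference in mortality, which is a secondary outcome and also the first halting parameter in 9.8.3.

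**Working it through.** **1. The plan's own figures.** No power is stated for the comparisons at issue. The only mortality power figure is in 9.8.3: 60 subjects, survival .600 v .976, HR .048, 13 events, 90% power, alpha .05. The Freedman log-rank formula gives:

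- HR = ln(.976)/ln(.600) = .048
- Events = (1.960 + 1.282)² × [(1 + HR)/(1 − HR)]² = 10.51 × 1.210 = 12.7, so 13
- N = 2 × 12.71/(2 − .600 − .976) = 59.96

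This reproduces the first row. The second row (.550 v .950) gives HR .086, 15 events and N = 59.3, against a stated .089 and 16; rounding of a survival figure would explain the gap. For the primary endpoint in 12.1 (.80 v .95, N = 160), HR = .230 and z = √(160 × .25/2) × (1 − .230)/(1 + .230) − 1.960 = .84, which is 80.0% power, as stated. The planning is therefore on a log-rank basis.

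**2. How far censoring times spread.**

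- One year: in 12.6.1.6 "The starting point will be the date of randomization and the end point will be date of death", but censoring is at one year post-transplant. Randomization falls 0-10 days after transplant (5.4.2), so survivors' times run from about 355 to 365 days.
- Closure: accrual takes about 3.5 years and closure comes 2 years after the last enrolment (section 4), so survivors are censored at about 2 to 5.5 years.

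**3. Hand check, one year.** Assume one-year survival of .80 v .94 with 88 per arm. Expected deaths are 88 × .20 + 88 × .06 = 22.9, leaving about 153 survivors. The rank sum variance is proportional to (n + 1) − Σ(c³ − c)/[n(n − 1)], where c is the size of each tied group.

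- All survivors tied: 177 − (153³ − 153)/(176 × 175) = 177 − 116.3 = 60.7
- Survivors spread over 11 days, about 14 per day: 177 − 1.0 = 176.0

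The expected rank difference hardly changes, so z shrinks by √(176.0/60.7) = 1.70. Simulated power with ties is 80.5%, a mean z of 1.96 + .86 = 2.82. Dividing by 1.70 gives 1.66, and power is Φ(1.66 − 1.96), about 38%. Simulation gives 36%.

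**4. Simulation.** N = 176 at 1:1, two-sided .05, exponential survival, 1,000 replicates (standard error at most 1.6 points). All survival rates are assumptions. One-year rows use the 0-10 day offset; closure rows use censoring uniform over 2-5.5 years.

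| Endpoint | Assumed 1-year survival | Log-rank | Gehan-Breslow | Ordinary rank sum |
|---|---|---|---|---|
| One year | .80 v .94 | 79.4% | 79.6% | 36.2% |
| One year | .85 v .97 | 83.7% | 83.1% | 30.0% |
| One year | .85 v .95 | 62.0% | 61.6% | 21.2% |
| One year | .75 v .91 | 81.8% | 80.9% | 43.1% |
| Closure | .80 v .89 | 83.9% | 78.5% | 66.4% |
| Closure | .85 v .925 | 82.0% | 76.0% | 57.2% |
| Closure | .90 v .96 | 83.3% | 79.2% | 46.7% |
| Closure | .95 v .985 | 71.2% | 68.1% | 22.6% |

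**5. Sensitivity.**

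- One-year survivors all tied, no dropout: no loss in any of the four rate pairs (for example 80.7% v 80.5%).
- Tied with 5% loss to follow-up: .80 v .94 gives 79.6% v 64.5%. Over the four pairs, the ordinary test keeps 71-87% of the log-rank power.
- Closure with a decreasing hazard (Weibull shape 0.5): log-rank 42-58%, ordinary rank sum 10-35%, Gehan-Breslow within about 2 points of log-rank.
- Equal survival of .90 in both arms: rejection rates of 4.0-6.0% for all three tests.

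**The case against.** The strongest reply is that the plan's vocabulary points to a censored-data test. It says Mann-Whitney for total G-CSF doses (12.7.2.2) and for T-cell responders (12.7.3.1), and keeps rank sum for time-to-event comparisons; 12.7.2.2 uses both terms side by side. In the four main sections the object compared is a pair of survivor functions with stated censoring. A Gehan-Breslow Wilcoxon, or loose naming of the log-rank family, is thus a plausible intention, and it would cost little.

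That much stands. A reader might infer that the plan specifies a test that ignores censoring and roughly halves the power. The documents do not support this as fact: the test is not defined, no mortality rates are given for these analyses, and under the literal reading the loss runs from none to more than two thirds. A reader might also infer that ranks mainly reflect enrolment date throughout. That applies to the closure analyses only; in 12.6.1.6 the spread comes from the gap between transplant and randomization, and from any dropout.

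The scope is limited too. Secondary graft loss uses CMH (12.6.1.5), retransplantation or death uses Cox (12.7.1.5), and both mortality sections also have a log-rank test by stratum. None of this identifies the unstratified test, and 12.7.1.2 and 12.7.1.4 name no log-rank test at all.

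**Conclusion.** The point holds as an unidentified and inconsistent test name with a conditional cost. If an ordinary rank sum test were run on follow-up times, power could fall from about 60-85% to about 20-65% under the assumed rates, exponential survival, 176 subjects and the follow-up pattern in step 2. If a Gehan-Breslow test was meant, the loss is about 0-6 points.

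The risk is a missed difference rather than a false positive, since type I error stays near 5% when censoring is alike in the two arms. The primary CMH analysis is unaffected, and no stated design figure is invalidated. Of the four main sections only one-year mortality is a secondary endpoint; the others, and the G-CSF and antibody comparisons, are exploratory.

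**What to change.** Replace the rank sum test with the log-rank test in 12.6.1.6, 12.7.1.2, 12.7.1.4 and 12.7.1.6, and for time to G-CSF (12.7.2.2) and time to late CMV disease by antibody status (12.7.3.2). For the comparisons between arms, give both the unstratified test and the test stratified by lymphocyte-depleting induction and dialysis at randomization, matching 12.7.1.1. The antibody comparison is not between arms and needs only the unstratified test.

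The cost is wording only: no new data, no change in sample size, and no effect on the primary analysis. The change should be made before anyone sees outcome data by arm.
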